8.1 Primary Endpoint

The primary endpoint for the randomized trial will be oral cancer-free survival.

8.2 Planned Secondary Endpoints and Analytical Methods

8.2.1 The size (bi-dimensional measurements) of oral IEN will be assessed and will be correlated with reduction in cancer risk. All oral lesions will be numbered and drawn onto a standardized diagram.

8.2.2 Toxicities associated with therapy will be assessed during the active treatment period. We will employ a rigorous monitoring plan for all participants and will include frequent clinic visits, assessment of symptoms, surveillance labs and measurement of drug trough levels.

8.2.3 We will assess molecular markers for correlations with oral cancer development in our oral leukoplakia patients. They will include (but are not restricted to):

8.2.3.1 EGFR, phospho-EGFR, TGF- α , ERK1/2, phospho-ERK1/2, AKT, phospho-AKT, COX-2, STAT3, phospho-STAT3, cyclin D1, HER2, Ki67, TUNEL, RAR-beta, hTERT, E-cadherin, P-cadherin, vimentin, Src, phospho-Src, cytokeratin. All these markers will be assessed in oral tissue biopsy specimens via immunohistochemistry laboratory analyses, except for RAR-beta and hTERT, which will be assessed via RNA in situ hybridization.

8.2.3.2 EGFR gene copy number, will be measured by real-time Q-PCR.

8.2.3.3 PGE₂ levels. This marker will be measured by high-performance liquid chromatography (HPLC) mass-spectrometry in frozen oral tissue biopsy specimens.

8.2.3.4 Perform computerized DNA image analysis of DNA content and ploidy evaluation and interpretation

8.2.3.5 Promoter methylation in p16 and in FHIT. These markers will be assessed via methylation-specific PCR (MSP) in oral tissue biopsy specimens.

8.2.3.6 Protein profiling, which will be assessed via SELDI mass-spectroscopy in serum specimens.

8.2.3.7 Chromosome-9-related levels of chromosome polysomy, chromosome index, and fraction of cells involved in subclonal outgrowth. These markers will be determined via chromosomal in situ hybridization (CISH) in oral tissue biopsy specimens.

8.2.3.8 BPDE-induced genetic damage, which will be measured by the Komet 4.0 image system in peripheral blood lymphocytes.

- 8.2.3.9 Estimated frequencies of polymorphisms in the following DNA-repair genes implicated in the nucleotide excision repair (NER) pathway: ERCC1, XPC, XPD/ERCC2, EXPF/ERC4, XPA, RAD23B, CLNH, ERCC5, LIG1. These polymorphisms will be assessed via DNA extraction and genotyping techniques in peripheral blood lymphocytes.
- 8.2.3.10 Frequencies of BPDE chromosomal aberrations on 3p12.3, 3p14.2, 3p21.3 and 3p25.2. These markers will be determined by fluorescence in situ hybridization (FISH) with several probes on 3p in peripheral blood lymphocytes.
- 8.2.3.11 Polymorphisms of CYP1A1, CYP3A4, CCND1, COX-2, EGFR, and ErbB-2. These polymorphisms will be explored via DNA extraction and genotyping techniques in peripheral blood lymphocytes.
- 8.2.3.12 Genome wide single nucleotide polymorphisms, telomere length, mitochondrial DNA alterations

8.2.4 Other Time-to-Event Endpoints

- 8.2.4.1 Overall survival. Overall survival is defined as time from randomization to death of any cause. If patients are alive at the end of study, the censoring time is set at the last follow up time.
- 8.2.4.2 Cancer-specific survival. Cancer-specific survival is defined as time from randomization to cancer specific death. If patients die of non-cancer cause or are alive at the end of study, the censoring time is set at the non-cancer death date or the last follow-up time.

8.3 Off Agent Criteria

Patients who have been included may discontinue the study agent for general reasons (Declaration of Helsinki) or for safety reasons. A patient has the right to discontinue the study agent without having to give an explanation and without any negative effect on further treatment.

All participants discontinuing the study agent prior to normal completion (normal completion will be defined as 12 consecutive months from study treatment initiation) will be asked to return to the study site for all remaining clinic visits and follow-up visits according to the schedule of events (Section 7.1), except for patients discontinuing treatment due to diagnosis of oral cancer.

Patients may stop taking study medications for the following reasons:

- Completed the protocol-prescribed intervention
- Adverse event or serious adverse event that is unacceptable to the patient or physician
- Repeated grade 2 or greater toxicities or grade 4 toxicity that is believed to be possibly, probably or definitely related to study medication
- Disease progression requiring alternative therapy in the opinion of the Principal Investigator

- Pregnancy
- Inadequate agent supply
- Allergic reaction to the study medication(s)
- Noncompliance
- Patient desire to stop taking medication
- Concomitant medications or medical contraindications.

Patients may resume treatment if the following criteria are met:

- Patients are within the normal treatment period (i.e. within 12 consecutive months from treatment initiation)
- The reason for treatment discontinuation was not a grade 4 toxicity determined to be possibly, probably, or definitely related to the study treatment, or diagnosis of oral cancer
- There is no other reason for withholding the study treatment in the Principal Investigator's opinion

8.4 Off-Study Criteria

Patients may go off-study for the following reasons:

- The protocol intervention and any protocol-required follow-up period is completed
- Diagnosis of cancer
- Lost to follow-up
- Withdraw consent
- Death.

Patients that have been placed off study will be asked to return to the study site for an early termination visit according to the schedule of events (Section 7.1).

8.5 Study Termination

The NCI or regulatory agencies may discontinue the investigation at any time.

9. REPORTING ADVERSE EVENTS

Definition: An adverse event (AE) is an untoward medical occurrence in a study participant. An AE does not necessarily have a causal relationship with the treatment or study participant. An AE can therefore be any unfavorable and unintended sign (including an abnormal laboratory finding), symptom or disease temporally associated with participation in a study, whether or not related to that participation. This includes all deaths that can occur while a participant is on a study. The NCI Common Toxicity Criteria (v3.0CTCAE), Appendix E) will guide grading of adverse events and dose reductions.

A list of adverse events that have occurred or might occur can be found in Section 6.2.

9.1 Adverse Events

9.1.1 Reportable Adverse Events

All adverse events that occur after the informed consent is signed and within 30 days after the last dose of study drug must be recorded on the adverse event source document whether or not related to study agent. Adverse events will be spontaneously reported by the patients,

observed by the investigators, or elicited by the investigator by asking the patients specific questions according to a predefined scheme. The investigator is responsible for assuring that there are procedures and expertise available to deal with emergency situations during procedures related to the study.

9.1.2 AE Data Elements

- Verbatim description of event
- Severity of AE
- Event onset date and ended date of AE (duration)
- Relationship to study drug
- Whether or not the event was reported as a Serious Adverse Event (SAE)

9.1.3 Severity of AEs

Adverse events not listed in the NCI Common Toxicity Criteria (v.3.0) will be assessed according to their impact on the participant's ability to perform daily activities as follows:

Severity	Description
Mild	
 • Barely noticeable, does not influence functioning • Causing no limitations of usual activities
Moderate	
 • Makes participant uncomfortable, influences functioning • Causes some limitations of usual activities
Severe	
 • Severe discomfort, treatment needed • Severe and undesirable, causing inability to carry out usual activities
Life Threatening	
 • Immediate risk of death • Life threatening or disabling
Fatal	
 • Causes death of participant

9.1.4 Follow-up of Adverse Events

All adverse events, including lab abnormalities that in the opinion of the investigator are clinically significant, will be followed according to good medical practices and documented as such.

9.2 Serious Adverse Events

9.2.1 Definition: ICH Guideline E2A and Fed. Reg. 62, Oct. 7, 1997 define serious adverse events as those events, occurring at any dose, which meet any of the following criteria:

- Results in death
- Is life threatening (*Note: the term life-threatening refers to an event in which the patient was at risk of death at the time of the event; it does not refer to an event which hypothetically might have caused death if it were more severe*).
- Requires inpatient hospitalization or prolongation of existing hospitalization
- Results in persistent or significant disability/incapacity

- Is a congenital abnormality/birth defect
- Events that may not meet these criteria, but which the investigator finds very unusual and/or potentially serious, will also be reported in the same manner

9.2.2 Reporting Serious Adverse Events

All participating centers will report SAEs to their respective IRBs within 5 working days of knowledge of the event and will simultaneously submit a copy of the SAE report to the IND sponsor (MDACC). Each center will report all deaths to their respective IRBs within 24 hours of knowledge of the event and will simultaneously submit a copy of the SAE report to the IND sponsor (MDACC). The IND sponsor will notify the NCI and OSI Pharmaceuticals within 24 hours of learning of the SAE to the following contacts:

- OSI Pharmaceuticals: fax to OSI Drug Safety at [contact] (for questions related to safety reporting, call OSI Drug Safety at [contact])
- NCI: fax [REDACTED]
- MDACC: Please email the SAE form to [contact] (E-mail must be sent from the PI's email address or the PI must be copied on the e-mail containing the form).
For problems sending the form or other questions, please contact [REDACTED]

The IND sponsor will also process and submit any required safety information to the FDA as required by CFR 312.32 "IND Safety Report."

All adverse events will be followed until the patient outcome has been established. To ensure the safety of study participants, all SAEs will also be reported to the Data and Safety Monitoring Board (DSMB) at M. D. Anderson Cancer Center.

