6.2 Reported Adverse Events and Potential Risks

Erlotinib

Based on clinical results, rash (dermatosis), diarrhea, nausea, fatigue, stomatitis, vomiting, and headache were the most frequently reported toxicities with exposure to single-agent erlotinib. Patients receiving erlotinib in combination with various chemotherapy agents have generally experienced the same type of adverse events as with either agent alone.

Common adverse events (occurring in 10%-25% of subjects) include dry or itchy skin, desquamation, dry eyes, decreased blood counts (which may lead to infection, bleeding and/or fatigue), dry mouth, nausea and vomiting, and anorexia.

Laboratory abnormalities observed infrequently with erlotinib as a single agent primarily involve liver function tests, including elevation of ALT, AST, and/or bilirubin.

There have been infrequent reports of serious interstitial lung disease (ILD)-like events (including fatalities) in patients receiving erlotinib for treatment of NSCLC, pancreatic cancer or other advanced solid tumors. In a single-agent study in patients with NSCLC, the incidence of ILD-like events (0.8%) was the same in the placebo and erlotinib groups. In a combination study with gemcitabine in patients with pancreatic cancer, the incidence of ILD-like events was 2.5% versus 0.4% in the erlotinib plus gemcitabine versus the placebo plus gemcitabine groups, respectively. The overall incidence in erlotinib-treated patients from all studies (including uncontrolled studies and studies with concurrent chemotherapy) is approximately 0.7% out of approximately 4,900 patients. Reported diagnoses included pneumonitis, radiation pneumonitis, hypersensitivity pneumonitis, interstitial pneumonia, interstitial lung disease,

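### Section 9.2.2 ties the IND sponsor's copy of a non-fatal SAE to the IRB submission, so the sponsor may learn of a life-threatening event up to 5 working days after the site does

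*Combined protocol and SAP*

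**What the plan says.** Section 9.2.2 sets two limits for the sites. For SAEs in general, centers "will report SAEs to their respective IRBs within 5 working days of knowledge of the event and will simultaneously submit a copy" of the report to the IND sponsor. For deaths the limit is shorter: "Each center will report all deaths to their respective IRBs within 24 hours of knowledge of the event", again with the sponsor's copy sent at the same time.

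The next step has its own clock: "The IND sponsor will notify the NCI and OSI Pharmaceuticals within 24 hours of learning of the SAE". This covers every SAE, fatal or not. For the regulator, "The IND sponsor will also process and submit any required safety information to the FDA as required by CFR 312.32". For the monitoring board, "all SAEs will also be reported to the Data and Safety Monitoring Board (DSMB) at M. D. Anderson Cancer Center"; Section 9.2.2 gives no time for that step.

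Section 9.2.1 defines seriousness. Besides death, its criteria include "Is life threatening" and "Requires inpatient hospitalization or prolongation of existing hospitalization".

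**The concern.** The sponsor's copy has no clock of its own. It travels with the IRB report, so the IRB's limit becomes the sponsor's limit. A patient at immediate risk of death falls under the same 5 working days as a routine hospital admission, because the only faster tier is for events that have already proved fatal.

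The section treats speed as important at the second step, where the sponsor has 24 hours to pass on any SAE, but that clock starts only when the sponsor learns of the event. The slow link is the first one, and everything that depends on the sponsor waits for it: notice to NCI and the supplier, and any safety report to the FDA.

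This matters because each center reports to its own IRB, and within Section 9.2.2 the sponsor is the point where reports from all five centers meet. Participants take a preventive agent daily for 12 months (Section 5.1). Section 6.2 records serious interstitial lung disease (ILD)-like events, some fatal, in patients given erlotinib and does not exclude a causal role. Section 10.1 lists ILD and liver toxicity for special attention. Until the sponsor is told, it cannot compare an event at one center with events elsewhere or alert the others.

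**Working it through.** No sample-size, power or alpha figure bears on this point. The check follows the reporting chain and converts the limits to calendar days.

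**Inputs**

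- Site to IRB and sponsor, SAEs in general: 5 working days from site knowledge (Section 9.2.2).
- Site to IRB and sponsor, deaths: 24 hours (Section 9.2.2).
- Sponsor to NCI and supplier: 24 hours from when the sponsor learns (Section 9.2.2).
- Randomizations per quarter: 8, 18, 22, 22, 18, 18, 18, 18, 8, total 150 (Section 4.4, Table 1).

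**Step 1: which clock applies.** Life-threatening events and hospitalizations are SAEs under criteria separate from death (Section 9.2.1). Section 9.2.2 singles out deaths only, so both fall under 5 working days. The contact list in Section 9.2.2 has an entry for the sponsor institution, but the 24-hour sentence above it binds the sponsor, not the sites, and the entry sets no time.

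**Step 2: working days to calendar days.** Counting the day of knowledge as day 0, five working days from any weekday span one weekend: 5 + 2 = 7 calendar days. From a Saturday it is 6 and from a Sunday 5. With a Monday holiday in the window it is 8 to 10. If the day of knowledge counts as day 1, it is 4 to 6 without a holiday.

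**Step 3: the chain under the current text and under a 24-hour site limit** (weekday knowledge, no holiday)

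| Recipient | Current maximum | With 24-hour site limit |
|---|---|---|
| IND sponsor | 7 days | 1 day |
| NCI and supplier | 7 + 1 = 8 days | 1 + 1 = 2 days |

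The longest permitted delay falls by 6 calendar days at each level.

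**Step 4: trial activity during the window, as context only.** A quarter is 365.25 / 4 = 91.3 days.

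- Slowest quarters: 8 × 8 / 91.3 = 0.7 patients randomized in 8 days.
- Fastest quarters: 22 × 8 / 91.3 = 1.9.
- Average over nine quarters: 150 × 8 / (9 × 91.3) = 1.5.
- On study drug at steady state, taking 2-year accrual and 12 months of treatment without discontinuation: 150 / 2 × 1 = 75, half of them on erlotinib.

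These figures describe who is in the trial during the window. They do not count people affected by the delay.

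**The case against.** The strongest reply is that Section 9.2.2 is internally consistent. It has one tier for deaths and one for other SAEs, and no passage sets 24 hours as the site standard for non-fatal events. That stands. A reader might infer that reports are late, or that a rule is broken; the documents do not support this. Five working days is a permitted maximum, and sites may report sooner.

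A reader might also infer that the affected patient stays on drug while the report is pending. The documents say otherwise. Section 10.1 has treatment held for sudden unexplained lung symptoms, before any diagnosis, and Section 10.3 has it held for grade 3 or 4 toxicity. Neither waits for the sponsor. Emergency unblinding under Section 6.5 would also bring the sponsor in early, but only if it is requested.

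Nor can the 1 to 2 patients randomized in the window, or the 75 on drug, be read as the effect of the delay. They would be randomized or treated anyway unless a single SAE paused the trial, and no passage available here says that it would. Section 11 makes discontinuation a decision of the sponsor and NCI, which then goes to the IRBs.

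The ILD background is also modest. Section 6.2 gives 0.8% in both arms of a single-agent lung cancer study and about 0.7% overall. At 0.7%, 75 erlotinib patients yield 75 × 0.007 = 0.5 expected events in the whole trial, so two ILD events to connect within one week would be unusual. This weakens ILD as an example. It leaves the reporting rule as it is, since the rule covers every kind of life-threatening event.

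Finally, it is tempting to say that the DSMB has no reporting limit at all, or that no shorter site limit exists anywhere. That goes too far. The contents page lists Appendix C (the DSMB charter) and Appendix F (adverse-experience reporting guidelines at the sponsor institution), and neither was available for this review. Section 9.2.2 refers to neither, but either could contain a limit.

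**Conclusion.** The point holds as a specific and inexpensive safety improvement. As Section 9.2.2 is written, a site complies while informing the sponsor of a life-threatening event about 7 calendar days after learning of it, with NCI and the supplier following at about day 8. The limit the section already uses for deaths would make these 1 and 2 days.

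The cost of the present wording is slower cross-site awareness on behalf of other patients. It falls mainly on events at the four other centers: the sponsor institution is itself a site and expects to accrue most of the patients (Section 4.4), although the text applies to all centers alike.

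The conclusion assumes that the day of knowledge is day 0, that no holiday intervenes, that the site uses its full allowance, and that Appendices C and F set no shorter limit. It relies on no outside regulatory deadline.

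**What to change.** In Section 9.2.2, separate the sponsor's copy from the IRB submission. Suggested text: *Each center sends the SAE report to the IND sponsor within 24 hours of learning of the event, independently of the IRB submission.* At minimum this should cover life-threatening SAEs. Covering all SAEs is preferable, because the sponsor's onward 24-hour duty already does and sites would then have one rule. Leave the IRB limit at 5 working days.

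Before amending, check Appendix F for a shorter limit and, if there is one, cite it in Section 9.2.2. Add a time limit for forwarding SAEs to the DSMB only if Appendix C does not already set one.

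The cost is one sentence and a memo to the sites. The drawback is that some first reports will be incomplete and will need a follow-up form. No dose, treatment or stopping rule changes.

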10. MANAGING ADVERSE EVENTS/TOXICITIES/EARLY TERMINATIONS

10.1 Adverse Events

Study participants will be monitored for all adverse events. All adverse events will be recorded in the source documentation.

Persons included in the study will be monitored for adverse events during telephone contacts and clinic visits. Patients will also be provided with a telephone number at which they can reach the study coordinator, research nurse or principal investigator. The range of adverse events possible in any clinical investigation is extensive and patients enrolled in this study will be carefully monitored. Particular attention will be paid to

- a) Diarrhea
- b) Rash
- c) Psychological side-effects as insomnia
- d) Signs and symptoms of ILD

- e) Eye disorders
- f) Anorexia
- g) Nausea
- h) Vomiting
- i) Hepatotoxicity

Potential hepatotoxicity from erlotinib will be monitored with periodic liver function testing (transaminases, bilirubin, and alkaline phosphatase); erlotinib dose reductions, as described in Section 10.3, will be implemented if warranted by changes in liver function.

Management of Adverse Events:

Skin rash or dermatosis has been observed during the first several days of treatment with erlotinib in many patients and has been noted to diminish in severity despite continued treatment. Patients who develop a rash characterized by pustules or raised red areas may be treated with oral minocycline (100 mg BID for 7–10 days to a maximum of 150 mg BID for 7–10 days as clinically indicated) at the discretion of the Investigator. Minocycline is known to interfere with anticoagulants and oral contraceptives. Patients treated with minocycline who are taking anticoagulants and/or oral contraceptives should be monitored accordingly.

Patients with acute onset of new or progressive, unexplained pulmonary symptoms such as dyspnea, cough, and fever should have treatment held pending diagnostic evaluation. If ILD is diagnosed, erlotinib should be discontinued and appropriate treatment instituted as necessary.

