10.3 Toxicity Attribution and Dose Reduction

Study medication will be held then restarted for grade 3 or 4 toxicities as outlined in the table below. If the patient experiences grade 3 toxicity on the

lowest doses, the patient will be taken off agent. There will be no dose escalation after dose reduction. Patients will not be taken off agent permanently if the SAE is clearly unrelated to the study medication. Dose reduction or stopping drug is also an option for grades 1 and 2 toxicities, irrespective of attribution to the study medication, that are unacceptable to the participant or physician.

Toxicity Attribution

Grade of Toxicity	Is Toxicity Associated with Drug Treatment				
	Unrelated	Unlikely	Possibly	Probably	Definitely
Grade 0	C	C	C	C	C
Grade 1	C	C	C	C	C
Grade 2	C	C	C	C	C
Grade 3	S-R ⁰	S-R ⁰	S-R ⁻¹	S-R ⁻¹	S-R ⁻¹
Grade 4	S-R ⁰	S-R ⁰	W	W	W

C = Continue drug

S-R⁰ = Stop drug until toxicity reaches grade 1 or lower, then restart drugs at the same doses

S-R⁻¹ = Stop drug until toxicity reaches grade 1 or lower, then restart drug at the next lower dose level (100 mg QD for erlotinib). The most common adverse events associated with erlotinib are rash (the most frequent) and diarrhea. If these adverse events do not resolve after the initial dose reduction, second dose reductions of erlotinib to 50 mg po QD are acceptable. After the second dose reductions, no further reductions will be permitted and patients with returning toxicities will be removed from the study.

W = Withdraw from trial

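### Sections 6.2 and 10.1 say to discontinue erlotinib once interstitial lung disease (ILD) is diagnosed, but the 10.3 dose table has no ILD exception and, read literally, directs a restart after most grade 3–4 cases

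*Combined protocol and SAP*

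**What the plan says.** **The ILD rule (6.2 and 10.1).** Section 10.1 says that patients with new, unexplained pulmonary symptoms "should have treatment held pending diagnostic evaluation". It then adds: "If ILD is diagnosed, erlotinib should be discontinued and appropriate treatment instituted as necessary". Section 6.2 has the same instruction, with *interrupted* in place of *held* for the period before diagnosis. Neither section conditions the instruction on grade or attribution.

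**The dose table (10.3).** The general rule is: "Study medication will be held then restarted for grade 3 or 4 toxicities as outlined in the table below". For grade 3 events judged unrelated or unlikely, and for grade 4 events judged unrelated or unlikely, the code means: "Stop drug until toxicity reaches grade 1 or lower, then restart drugs at the same doses". For grade 3 events judged possibly, probably or definitely related it means: "Stop drug until toxicity reaches grade 1 or lower, then restart drug at the next lower dose level (100 mg QD for erlotinib"). Related grade 4 events mean withdrawal. The text above the table gives one limit at grade 3: a patient with grade 3 toxicity on the "lowest doses, the patient will be taken off agent". It also says: "Patients will not be taken off agent permanently if the SAE is clearly unrelated to the study medication". ILD is not mentioned anywhere in 10.3.

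**Resumption (8.3).** A patient who has stopped may resume if three conditions hold: the 12-month treatment window is still open; the reason for stopping was neither a related grade 4 toxicity nor oral cancer; and the Principal Investigator sees no other reason to withhold treatment. ILD is not named.

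**The concern.** The protocol has a diagnosis-specific stopping rule and a general restart rule that both cover the same patient, and it does not say which prevails. A site that treats the 10.3 table as the operative instruction would, after recovery, give erlotinib again to a patient with diagnosed ILD. At grade 3 this does not require a wrong attribution, because even an event judged definitely related is coded as a restart at a lower dose.

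The stakes lie in the nature of the event. Section 6.2 reports that ILD-like events on erlotinib have included deaths and that a causal role cannot be completely excluded. Criterion 4.2.8 bars entry to anyone with a documented history of ILD, so the literal table would re-dose a patient whose new diagnosis would have kept them out of the trial. This is a prevention trial, and five centers have to apply the rule in the same way.

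**Working it through.** This is mainly a question of consistency between sections. The arithmetic only sizes it. The plan gives no figure of its own for this point.

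**Step 1. Apply the 10.3 table to diagnosed ILD.**

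| Grade | Unrelated / unlikely (2 cells) | Possibly / probably / definitely related (3 cells) | Agrees with a lasting stop? |
|---|---|---|---|
| 3 | Restart, same dose | Restart, next lower dose (off agent if already on the lowest) | No, apart from the lowest-dose limit |
| 4 | Restart, same dose | Withdraw | Only the 3 related cells |

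Of the 10 grade 3–4 cells, 5 + 2 = 7 direct a restart once the event is grade 1 or lower, and 3 direct withdrawal. At grades 1–2 the table says continue, but 10.3 also makes stopping an option there, so I claim no conflict at those grades.

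**Step 2. Is the grade 4 restart path realistic?** Under 10.2, *unrelated* requires no reasonable temporal sequence, which is hard to assign to ILD arising on a daily drug. *Unlikely* is easier to reach: it includes events that other medication or environmental factors could readily produce. Section 6.2 says most reported cases had confounding or contributing factors, among them prior radiotherapy and pulmonary infection. An *unlikely* rating is therefore foreseeable.

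**Step 3. Does 8.3 close the gap?** Take a grade 3 ILD judged definitely related, recovered to grade 1 inside the 12-month window. The first condition is met. The second is met, because the event was neither a related grade 4 toxicity nor oral cancer. Only the third, the Principal Investigator's opinion, can stop the restart.

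**Step 4. Is *discontinued* permanent?** Sections 6.2 and 10.1 contrast a temporary step before diagnosis with discontinuation after it, which points to a lasting stop. That is an inference: neither section says so outright, and 8.3 uses discontinuation for stops that can be resumed.

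**Step 5. Size.** Inputs: 0.7% of about 4,900 erlotinib-treated patients (6.2); 0.8% in a single-agent study (6.2), the same in its placebo and erlotinib groups; 75 patients on erlotinib (Section 3).

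- Cases behind the pooled rate: 0.007 × 4,900 ≈ 34; exact 95% interval for the rate 0.48% to 0.97%.
- Expected ILD cases of any grade: 75 × 0.007 = 0.525; over the interval, 75 × 0.0048 = 0.36 to 75 × 0.0097 = 0.73.
- Chance of at least one case: 1 − 0.993^75 = 0.41.
- At 0.8%: 75 × 0.008 = 0.60 cases; 1 − 0.992^75 = 0.45.

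The documents do not split cases by grade or recovery. Let f be the assumed share of cases that fall in a restart cell and recover to grade 1 or lower within the window:

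| f (assumed) | Expected cases the table would restart | Chance of at least one |
|---|---|---|
| 0.10 | 0.525 × 0.10 = 0.05 | 1 − (1 − 0.0007)^75 = 0.05 |
| 0.50 | 0.525 × 0.50 = 0.26 | 1 − (1 − 0.0035)^75 = 0.23 |
| 1.00 | 0.525 | 0.41 |

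The last row is a mathematical ceiling and not a realistic value, since 6.2 reports deaths and some cases would be of other grades. The table counts cases to which the restart instruction could apply. It does not count re-exposures, because it makes no allowance for the ILD rule or for 8.3 preventing the restart.

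**The case against.** The strongest reply is that the protocol already gives the right instruction, twice, and once within Section 10 shortly before the table. A specific rule for a named diagnosis is normally read as governing over a general grade table. The drafting supports this: 10.1 sends liver toxicity to the table ("erlotinib dose reductions, as described in Section 10.3, will be implemented if warranted by changes in liver function") and does not send ILD there, and the reduced-dose note in 10.3 discusses rash and diarrhea. Section 8.3 lets a patient stop for an unacceptable adverse event or a medical contraindication, and it makes resumption permissive and subject to the Principal Investigator, a role held at M. D. Anderson, which is also the IND sponsor. If discontinuation can be resumed, there may be no contradiction at all.

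Most of that stands. A careful physician would probably not restart. What it does not supply is a statement of precedence. The stopping reasons in 8.3 are things a patient *may* do, the ILD rule says *should*, and the restart rule in 10.3 says *will*. The reply also works only if each site infers the intended order.

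Two stronger readings are tempting and are not supported:

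- A reader might infer that the protocol requires re-dosing after ILD, or that there is a 41% chance of a patient being re-exposed. The first ignores 6.2, 10.1 and the discretion in 8.3. The second treats every ILD case as restartable and every safeguard as failing.
- A reader might infer that nobody outside the site can stop a restart. Serious adverse events go to the sponsor and the data and safety monitoring board, and 8.3 gives the Principal Investigator the judgment on resumption. The board's charter (Appendix C) is listed but is not in the supplied text, so its powers cannot be judged from its absence here.

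**Conclusion.** The point holds as a missing exception, with no stated order of precedence between the ILD rule and the dose table. It is more than a missing detail, because 10.3 and 8.3 together would permit re-dosing after a potentially fatal toxicity that is itself an exclusion criterion.

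The size in patients is small. About 0.5 ILD cases of any grade are expected on erlotinib if the pooled 0.7% rate carries over, and re-exposures would be far fewer. That rate includes uncontrolled studies and concurrent chemotherapy, mostly in advanced cancer, whereas this trial excludes a history of ILD and active non-oral cancer, so the true figure may be lower. The 0.8% single-agent rate was no higher than on placebo, so it is not evidence of excess risk. The argument therefore rests on the severity of each event and not on frequency.

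Confidence is high that the exception is absent and low on how often it would matter. The primary endpoint, power and type I error are unaffected. I rate this a cheap improvement on patient-safety grounds.

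**What to change.** Add one note under the 10.3 table: *Exception: if ILD is diagnosed, discontinue study drug permanently regardless of grade or attribution (see 10.1) and continue follow-up under 8.3. This overrides the table and the sentence on clearly unrelated SAEs.*

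In 8.3, add diagnosed ILD to the named bars to resumption, beside related grade 4 toxicity and oral cancer.

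The cost is a few sentences in an amendment, with no added visits, staff or patients. The downside is that, rarely, a patient whose ILD was truly unrelated could not restart. That fits 10.1, which makes no exception for attribution.
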